6.4.4. SAS Code for Placebo-Based Imputation

A sensitivity analysis for the primary endpoint will be performed using placebo-based imputation for responses after treatment discontinuation. In this analysis, data occurring after treatment discontinuation will be set to missing and multiple imputation will then be performed using a regression method obtained only from placebo-treated participants with terms for baseline value and the randomization stratification variable.

The following is a partial SAS code for the placebo-based pattern imputation at Week 26:

```
proc mi data=ADEFF out=outmi seed=123 nimpute=1000; class trt01pn strat; var base strat Week26; monotone reg(/details); mnar model (Week26/modelobs=(trt01pn='Placebo')); run;
```

where trt01pn is the randomized treatment group, base is the proteinuria value at baseline, strat is the randomization stratification variable, and Week26 is the change from baseline in log(proteinuria) at Week 26.

The 1000 imputed data sets are then analyzed using ANCOVA (refer to Section 6.4.1 for SAS code) and PROC MIANALYZE procedure will be used to generate valid statistical inferences about these parameters.

6.4.5. SAS Code for Tipping Point Analysis

A sensitivity analysis for the primary endpoint will be performed using the tipping point approach where a search is conducted for a tipping point that reverses the study conclusion from being favorable to ALXN2050 to being unfavorable. For the tipping point sensitivity analysis, the missing data mechanism for the missing change from baseline in log proteinuria values at Week 26 will be considered to be missing not at random (MNAR). Imputations are performed for missing change observations for ALXN2050 treated participants assuming not the full treatment effect, but the treatment effect adjusted by a shift parameter delta. After obtaining complete data sets for multiple shift parameters, the complete data sets will be used in the MMRM analysis, and inferences from each complete dataset will be combined using SAS PROC MIANALYZE to obtain an overall test statistic for each shift value. Multiple shift parameters will be tested until the inference concludes that statistical significance disappears.

The following is a partial SAS code for the multiple imputation analysis for a specified shift parameter at Week 26:

```
proc mi data=ADEFF out=outmi seed=123 nimpute=1000;
class trt01pn strat;
monotone method=reg;
var trt01pn strat base Week26;
mnar adjust (Week 26 /shift=delta adjustobs=(trt01pn='ALXN2050'));
```

where trt01pn is the randomized treatment group, base is the proteinuria value at baseline, Week26 is the change from baseline in log(proteinuria), and strat is the randomization stratification.

The 1000 imputed data sets are then analyzed using ANCOVA (refer to Section 6.4.1 for SAS code) and PROC MIANALYZE procedure will be used to generate valid statistical inferences about these parameters.

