2. STATISTICAL HYPOTHESES

The primary hypothesis for this study is that ALXN2050 180 mg bid is superior to placebo in decreasing proteinuria. Hypothesis testing will be 1-sided and performed at the 0.05 level of significance for each disease cohort without adjusting for multiplicity.

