4.2.3. Sensitivity Analyses

Table 4 summarizes the sensitivity analyses that will be produced for the primary endpoint.

All sensitivity analyses will be based on an ANCOVA model using the FAS population; in addition sensitivity analysis due to dosing pause will be repeated on PPS population.

Population of no impact by dosing pause will be defined as the participants who have at least one valid 24-hour urine collection obtained within 3 weeks prior to the Week 26 Visit before dosing pause.

Table 4: Sensitivity Analyses

Sensitivity Analysis	Applied Cohorts	Handling of Intercurrent Events/ Description	
Placebo-based multiple imputation + carry-forward	LN cohort only	Treatment discontinuation: Data collected on or after treatment discontinuation will be imputed using placebo-based multiple imputation. Receipt of additional standard of care therapy (LN cohort only): Data collected on or after receipt of additional standard of care therapy will be imputed using the value collected at the time of flare (carry forward).	
Placebo-based multiple imputation	LN and IgAN cohorts	Treatment discontinuation: • Data collected on or after treatment discontinuation will be imputed using placebo-based multiple imputation. Receipt of additional standard of care therapy (LN cohort only): • Data collected on or after receipt of additional standard of care therapy will be imputed using placebo-based multiple imputation.	
Tipping point analysis	LN and IgAN cohorts	Participants who receive additional standard of care therapy (LN cohort only), discontinue treatment, withdraw early, or die are assumed to have outcomes that are worse than otherwise similar participants who remain in the study or did not receive additional standard of care therapy or discontinue treatment.	

Table 4: Sensitivity Analyses

Sensitivity Analysis	Applied Cohorts	Handling of Intercurrent Events/ Description	
Per-randomized stratification analysis	LN and IgAN cohorts	Treatment discontinuation: Data collected on or after treatment discontinuation will be imputed using multiple imputation. Receipt of additional standard of care therapy (LN cohort only): Data collected on or after receipt of additional standard of care therapy will be imputed using the value collected at the time of flare (carry-forward).	

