Sensitivity analysis due to dosing pause- excluding data points impacted by dosing pause	LN and IgAN cohorts	Dosing pause will be regarded as an intercurrent event, in which the analysis is similar to that of treatment discontinuation.	
Sensitivity analysis due to dosing pause- excluding participants impacted by dosing pause	LN and IgAN cohorts	The participants in the population of no impact by dosing pause will be included.	

Abbreviations: IgAN = immunoglobulin A nephropathy; LN = lupus nephritis

Further details of these sensitivity analyses are below.

- Placebo-based multiple imputation + carry-forward: The primary endpoint will be analyzed in the same manner as the primary analysis, except that data collected on or after treatment discontinuation will be assumed missing and imputed using placebobased multiple imputation where it will be assumed that outcomes occurring after treatment discontinuation will follow the trajectory of outcomes similar to the one in the placebo treatment group, taking into account observed values prior to treatment discontinuation (Ratitch, 2014).
- Placebo-based multiple imputation: The primary endpoint will be analyzed in the same manner as the primary analysis, except data collected on or after treatment discontinuation or receipt of additional standard of care therapy (LN cohort only) will be assumed missing and imputed using placebo-based multiple imputation.
- Tipping point analysis: An additional sensitivity analysis will be performed based on the delta-adjusted stress testing method (tipping point analysis). This approach assumes that participants who discontinue from ALXN2050 treatment or who receive additional standard-of-care therapy (for the LN cohort only) experience worsening, defined by a prespecified adjustment (delta) in the primary efficacy endpoint compared with the observed efficacy score of participants who continue the study to the next visit. For each value of delta, the treatment effect will be determined, and the value of delta for which the nominal 2-sided p-value crosses 0.10 will be considered

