Expected changes in proteinuria and associated variability were not available on the log-scale for LN; however, 2 studies of participants with LN who were treated with mycophenolate mofetil (MMF) showed mean proteinuria values of approximately 4 g/day at baseline and approximately 2 g/day at Week 24 (Appel, 2009; Ginzler, 2005). The GM of the ratio of 26-week to baseline proteinuria values is assumed to be 0.60 (ie, a 40% reduction from baseline in proteinuria) for the placebo group. In order to target at least a 30% relative treatment effect (ie, 1 minus GMR of ALXN2050 180 mg bid to placebo at Week 26), the GM of ratio of 26-week to baseline is assumed to be 0.40 (ie, a 60% reduction from baseline in proteinuria) for the ALXN2050 180 mg bid group. The log change from baseline in proteinuria is calculated as log (0.60) and log (0.40) for the placebo and ALXN2050 180 mg bid treatment groups, respectively, for the LN cohort. A common SD of log change is assumed to be 0.60 (Fellström, 2017). Under these assumptions and an anticipated 10% drop out rate, a sample size of 60 participants (30 participants randomized to ALXN2050 180 mg bid, 30 participants randomized to placebo) in the LN cohort will provide approximately 80% power to detect a treatment difference with a 1-sided significance level of

0.05. An additional 10 participants will be enrolled in the ALXN2050 120 mg bid treatment group for a total of 70 participants in the LN cohort.

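### The SAP gives three different rules for whose values the tipping-point analysis shifts; if placebo is shifted too, the tipping delta roughly doubles at the planned 10% missing per arm

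*SAP*

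**What the plan says.** The tipping-point analysis of the primary endpoint is described in three places.

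- **SAP 4.2.3, Table 4.** Those who receive additional standard of care therapy (LN only), discontinue treatment, "withdraw early, or die are assumed to have outcomes that are worse than otherwise similar participants who remain in the study". No arm is named.
- **SAP 4.2.3, text below the table.** The approach assumes that "participants who discontinue from ALXN2050 treatment or who receive additional standard-of-care therapy (for the LN cohort only) experience worsening". Discontinuers are limited to ALXN2050; additional-therapy recipients are not. The continuation refers to participants who drop out, again with no arm.
- **SAP 6.4.5.** "Imputations are performed for missing change observations for ALXN2050 treated participants assuming not the full treatment effect". The sample code shifts a treatment level named ALXN2050. The ANCOVA code in 6.4.1 has three levels: 120 mg, 180 mg and placebo.

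On the model, 6.4.5 says "the complete data sets will be used in the MMRM analysis" and closes by sending the same data sets to ANCOVA. SAP 4.2.3 has the general rule: "All sensitivity analyses will be based on an ANCOVA model using the FAS population".

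The stopping criterion is the "value of delta for which the nominal 2-sided p-value crosses 0.10". This matches SAP section 2: "Hypothesis testing will be 1-sided and performed at the 0.05 level of significance for each disease cohort". No range for delta is given, and the plausibility of the tipping value is left to clinical judgment.

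In the primary analysis (SAP 4.2.2 and 6.4.1), values after discontinuation are multiply imputed under missing-at-random (MAR). In LN, the 24-hour value at renal flare is carried forward after additional therapy.

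**The concern.** A tipping-point analysis asks how much worse the unobserved outcomes on drug would have to be before the result is lost. If placebo receives the same penalty, the two shifts cancel in the treatment difference, wholly or in part, and the question is no longer the one asked. Three rules that differ on arm and event cannot be programmed as one analysis, and someone would have to choose between them, possibly after seeing results.

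LN has a further gap. A carried-forward flare value is not missing, so a rule that shifts missing values passes over those participants, although both descriptions in 4.2.3 include them.

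At stake is the reported delta. The SAP judges robustness by whether that number is clinically plausible, so a rule that doubles it can change the conclusion drawn from the same data.

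**Working it through.** **Inputs (SAP section 5 unless stated).** LN uses "log (0.60) and log (0.40) for the placebo and ALXN2050 180 mg bid treatment groups", a difference of log(0.60/0.40) = 0.4055. For IgAN it is log(0.85/0.55) = 0.4353. The SD of log change is 0.60 and dropout is 10%, with no split by arm. Allocation is 30/10/30 in LN and 24/8/24 in IgAN (180 mg, 120 mg, placebo). The test is 1-sided at 0.05.

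**Reproducing the plan's own figure.** The SAP states no tipping value, so the check is on power, Φ(Δ / (σ√(2/n)) − 1.645). For LN with 27 evaluable per arm: 0.4055 / (0.60 × √(2/27)) = 2.483, giving 79.9%, which agrees with about 80%. For IgAN with 22 per arm: 0.4353 / (0.60 × √(2/22)) = 2.406, giving 77.7%; 80.7% needs 24 evaluable. The inputs are therefore read correctly. The IgAN shortfall is a separate matter.

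**Effect of delta on the difference.** With missing fractions f_A on drug and f_P on placebo:

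- ALXN2050 only: −Δ + f_A × delta
- both arms: −Δ + (f_A − f_P) × delta

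In LN with 3 of 30 missing per arm and delta = 1.1, the ALXN2050-only difference is −0.4055 + 0.10 × 1.1 = −0.296. With both arms shifted it stays at −0.4055 for every delta. The p-value then moves only because shifted values widen the spread within each arm.

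**Hand check, LN, 10% missing per arm.** Shifting a fraction f of an arm by delta adds f(1 − f) × delta² to its variance. Imputation adds 0.1656² − 0.36 × 2/30 = 0.0034 to the squared standard error (0.1656 is the simulated standard error at delta = 0).

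- ALXN2050 only, delta 1.1 (40 of 70 participants are in shifted arms): pooled variance 0.36 + (40/70) × 0.09 × 1.21 = 0.422; SE = √(0.422 × 2/30 + 0.0034) = 0.178; t = 0.296/0.178 = 1.66.
- Both arms, delta 2.2: variance 0.36 + 0.09 × 4.84 = 0.796; SE = √(0.796 × 2/30 + 0.0034) = 0.238; t = 0.4055/0.238 = 1.71.

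Both are close to the critical value of about 1.67.

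**Simulation.** Three-arm ANCOVA on baseline, with the observed difference fixed at the design effect and residual SD at 0.60. Missing Week 26 values were imputed under MAR, shifted and pooled by Rubin's rules, with delta raised in steps of 0.05 until the 2-sided p reached 0.10. Figures are medians over 60 to 80 data sets. Every split other than 10% per arm is an assumption.

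| Missing, 180 mg / placebo | ALXN2050 only | Both arms |
|---|---|---|
| LN 3/3 (10% each) | 1.1 | 2.2 |
| IgAN 2/2 (about 10% each) | 1.2 | 2.2 |
| LN 6/6 | 0.55 | 1.6 |
| LN 6/3 | 0.6 | 0.9 |
| IgAN 4/2 | 0.7 | 1.0 |
| IgAN 2/3 | 1.2 | about 3 |
| LN 3/6 | 1.05 | none up to 6 in 82% of data sets |
| IgAN 2/5 | 1.1 | none up to 6 in 90% of data sets |

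As multiples of proteinuria, exp(1.1) is about 3-fold and exp(2.2) about 9-fold. Across all the splits run with more missing on drug, the both-arm delta was 1.2 to 1.7 times the ALXN2050-only delta.

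**LN with additional therapy (assumed: 3/3 discontinue, 3/6 receive additional therapy).** The tipping delta is about 0.5 if only ALXN2050 participants are shifted, 1.5 under the text of 4.2.3 and about 4 under Table 4. This run imputed all affected values under MAR and did not carry flare values forward. It shows how far the rules diverge and does not forecast the trial's value.

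**The case against.** The best defence is that Table 4 is only a summary. The text below it is introduced as the further detail, and for discontinuers it agrees with 6.4.5 that only ALXN2050 is shifted. IgAN has no additional-therapy event, so there the two detailed descriptions agree and Table 4 is the outlier. That stands. It does not settle LN additional-therapy recipients: the text names no arm for them, and 6.4.5 read literally does not reach them.

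Four stronger readings are tempting, and the documents do not support them.

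- *The tipping point always doubles or disappears, so the analysis always supports robustness.* The size depends on a split of missing data that the plan does not give. With more missing on drug, the both-arm version still tips, at 1.2 to 1.7 times the delta. With equal missingness it still tips, through variance. It can vanish only with an assumed excess of missing data on placebo.
- *It is the only stress test that lets data be missing not at random.* Table 4 also plans placebo-based multiple imputation, in two forms for LN and one for IgAN, and the code in 6.4.4 uses a missing-not-at-random model. Neither form depends on the shift rule.
- *The model is undecided between MMRM and ANCOVA.* SAP 4.2.3 settles it as ANCOVA and 6.4.5 ends there too. With Week 26 as the only post-baseline visit modelled, the two give essentially the same estimate. The MMRM sentence is a slip.
- *The plan intends to shift placebo.* Only Table 4 can be read that way for discontinuers.

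It is also fair that this is one sensitivity analysis among several in a Phase 2 study whose primary analysis does not affect its own progression.

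**Conclusion.** The concern holds as an inconsistency in who is shifted. Following Table 4 would shift placebo for every event; following the text of 4.2.3 would shift placebo for LN additional-therapy recipients; and 6.4.5 leaves out LN participants whose flare value is carried forward.

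At the planned 10% missing, applied equally to each arm, shifting placebo moves the tipping delta from about 1.1 to 2.2 in LN and from about 1.2 to 2.2 in IgAN, and leaves the treatment difference where it was. These figures rest on the design effects, an SD of 0.60 and MAR imputation before the shift. Results for unequal splits rest on assumed splits as well.

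This is a should-fix point. It affects the only planned analysis that varies delta. It does not affect the primary analysis or the placebo-based imputation.

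**What to change.** State one rule, identically, in Table 4, the text of 4.2.3 and 6.4.5:

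1. In every arm, start from the value the primary analysis assigns: MAR-imputed after discontinuation, and the carried-forward flare value after additional therapy for renal flare. Delta = 0 then reproduces the primary analysis.
2. Add delta to those values in ALXN2050 participants only. Leave placebo unshifted.
3. Analyse by ANCOVA, and replace MMRM in 6.4.5.
4. Set `adjustobs` to levels of `trt01pn` that exist: 180 mg for the primary contrast, both doses for the pooled contrast.
5. Add delta to carried-forward values in a data step, because PROC MI shifts only values that it imputes.

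Step 1 matters. A simpler repair would set additional-therapy values to missing on ALXN2050 and leave placebo with carried-forward flare values, which handles the same event differently by arm. If 3 of 30 on drug received additional therapy with flare values 75% above baseline (an assumption), replacing those values by the expected change on drug would favour the drug by 3/30 × (−log 0.40 + log 1.75) = 0.10 × (0.92 + 0.56) = 0.15 log units before any shift.

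The cost is a few sentences, slightly more programming, and a tipping point that may look less favourable. The change should be made before unblinding.
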